The first radiological assessment of tumor response status will be performed at Week 6 (± 1 week), unless there is clinical indication warranting earlier radiologic imaging. If imaging at Week 6 shows irSD, treatment will be continued and tumor assessments will be conducted at the next regularly scheduled imaging time point, ie, at Week 12 (± 1 week). Responses (immune-related partial response [irPR] or irCR [complete response]) should be confirmed no less than 4 weeks after the initial response, but generally at the next scheduled tumor assessment time point.

If the time point tumor assessment is PD, treatment should continue and tumor assessments repeated at least 4 weeks later, but generally at the next scheduled tumor assessment time point in order to confirm immune-related progression disease (irPD). If repeat imaging shows a reduction in the tumor burden compared to the initial tumor assessment demonstrating PD, treatment may be continued as per treatment schedule. If repeat imaging confirms irPD, subjects will be discontinued from study treatment. In determining the tumor time point response, investigators should consider all target lesions as well as nontarget lesions and new lesions.

The decision to continue study treatment after the first evidence of PD is at the Investigator's discretion based on the clinical status of the subject as described in [Table 6](#) below.

Subjects may continue receiving study treatment while waiting for confirmation of PD if they are clinically stable as defined by the following criteria:

- Absence of signs and symptoms (including worsening of laboratory values) indicating disease progression
- No decline in ECOG PS
- Absence of rapid progression of disease
- Absence of progressive tumor at critical anatomical sites (eg, cord compression) requiring urgent alternative medical intervention

If irPD is confirmed and the subject is experiencing extraordinary clinical benefit, site must contact Sponsor to discuss continuing treatment.

Tumor assessments per modified RECIST 1.1 will follow Eisenhauer, et al. (2009), however, up to 10 target lesions, up to 5 per organ, may be selected (as opposed to the maximum of 5 target lesions, up to 2 per organ, mentioned in Eisenhauer, et al., 2009).

Table 6 Imaging and Treatment After First Radiologic Evidence of Progressive Disease

	Clinically Stable		Clinically Unstable	
	Imaging	Treatment	Imaging	Treatment

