Lesions with Prior Local Treatment	During target lesion selection the radiologist will consider information on the anatomical sites of previous intervention (eg, previous irradiation, RF-ablation, TACE, surgery). Lesions undergoing prior intervention will not be selected as target lesions unless there has been a demonstration of progression in the lesion.
Nonmeasurable (Nontarget) lesions	
Nontarget lesions will include:
 
 • Measurable lesions not selected as target lesions. There is no limit to the number of nontarget lesions that can be recorded at baseline • Other types of lesions that are confidently felt to represent neoplastic tissue, but are difficult to measure in a reproducible manner. These include bone metastases, leptomeningeal metastases, malignant ascites, pleural or pericardial effusions, ascites, inflammatory breast disease, lymphangitis cutis/pulmonis, cystic lesions, ill-defined abdominal masses, etc. • Multiple non target lesions from the same organ may be captured as a single item on the eCRF (eg, multiple liver metastases) 
Nontarget lesions should be reported as present at baseline

SOD_{baseline}	Sum of diameters at baseline = LDi of all non-nodal + SDi of all nodal target lesions
2. Time point Assessments After Baseline	
Target lesion measurements	
Locate image that optimizes the LDi of the non-nodal target lesion or SDi of target node(s). There is no need to go to an identical slice from baseline.
 
Measure the respective LDi and SDi for all target lesions and calculate time point SOD (SOD_{timepoint}).
 
Special consideration for target lesions:
 
 • If target lesion is too small to measure, a default value of 5mm should be entered on eCRF. • If target lesion is 5-10mm, actual diameter should be entered in the eCRF. • If target lesion splits into 2 or more lesion then the LDi of split lesions will be added and entered in place of that lesion. • If two target lesion merged to form one lesion than LDi of one should be entered as “0mm” while the other lesion should have the diameter of the merged lesion.

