Nontarget Lesion Assessment	Nontarget lesions are evaluated qualitatively as present, absent, not evaluable (NE) or unequivocal progression. The response of nontarget lesions primarily contributes to the overall response assessments of irCR. Nontarget lesions do not affect irPR and irSD assessments. Only a massive and unequivocal worsening of nontarget lesions alone, even in the presence of stable disease or a partial response in the target lesion is

	indicative of irPD. IrCR is not possible unless all nontarget lesions are absent.
Definition of New Lesion	
Any lesion that was not recorded at baseline. There is no minimum size criteria to identify a new lesion and clinical judgment must be used by the PI.
 
 • May include a lesion in an anatomical location that was not scanned at baseline (ie, brain) • Should be unequivocal and not due to differences in scanning technique • If equivocal, should be assessed at next time point; if present, irPD is the date the lesion was first seen (not the date confirmed)
3. irRECIST Overall Tumor Assessment	
irCR	
 • Complete disappearance of all measurable and nonmeasurable lesions (from baseline) and there are no unequivocal new lesions (unconfirmed irCR). • Lymph nodes must decrease to <10 mm in SDi. • Confirmation of response is required ≥ 4 weeks later, preferably at next time point, to be considered a confirmed irCR.
irPR	
 • If the SOD_{timepoint} of TLs decreases by ≥ 30 % compared to SOD_{baseline} and there are no unequivocal new lesions, and no progression of nontarget disease, it is an irPR (unconfirmed). • Confirmation is required ≥ 4 weeks later, preferably at next time point, to be considered a confirmed irPR.
irSD	
Failure to meet criteria for irCR or irPR in the absence of irPD.
 
 • If the sum of the TLs and the status of the nontarget lesions do not reach the criteria to meet irPR or irPD (increase $\geq 20\%$ and at least 5 mm absolute increase in SOD compared to nadir[†]) the response is irSD. • irSD = neither 30% decrease compared to SOD_{baseline} or 20% increase and at least 5 mm absolute change compared to nadir. • [†]SOD_{nadir}: Lowest measure SOD of TLs at any time point from baseline onward.

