irPD	
Minimum 20% increase and a minimum 5 mm absolute increase in SOD compared to nadir, or irPD for nontarget lesion(s) or unequivocal new lesion(s).
 
 • Confirmation of progression is recommended at a minimum of 4 weeks after the first irPD assessment (preferably at next tumor assessment time point). 
The decision to continue study treatment after the first evidence of PD is at the investigator's discretion based on the clinical status of the subject as described in table below

	Clinically Stable		Clinically Unstable	
	Imaging	Treatment	Imaging	Treatment
1st radiologic evidence of PD	Repeat imaging at ≥ 4 weeks (next TA time point) to confirm PD	May continue study treatment at the Investigator's discretion while awaiting confirmatory scans	Repeat imaging at ≥ 4 weeks to confirm PD per physician discretion only	Discontinue treatment
Subsequent scan confirms PD	No additional imaging required	Discontinue treatment	No additional imaging required	N/A
Subsequent scan shows SD, PR or CR	Continue regularly scheduled imaging assessments	Continue study treatment at the Investigator's discretion	Continue regularly scheduled imaging assessments	May restart study treatment if condition has improved and/or clinically stable per investigator's discretion

Subjects may continue receiving study treatment while waiting for confirmation of irPD if they are clinically stable as defined by the following criteria:
 
 • Absence of signs and symptoms (including worsening of laboratory values) indicating disease progression • No decline in ECOG performance status • Absence of rapid progression of disease • Absence of progressive tumor at critical anatomical sites (eg, cord compression) requiring urgent alternative medical intervention 
If irPD is confirmed and the subject is experiencing extraordinary clinical benefit, site must contact sponsor to discuss continuing treatment
				
irNE	Used in exceptional cases where insufficient data exists due to poor quality of scans or missed scans or procedure			

Derivation of irRECIST overall responses			
Measurable response	Non-measurable response		
Target Lesions (% change in SOD)^a	Nontarget Lesions Status	New Lesions Status	Overall Response (irRECIST)
↓100	Absent	Absent	irCR ^b
↓100	Present/NE	Absent	irPR ^b
↓ ≥ 30	Present/Absent/NE	Absent	irPR ^b

↓<30 to <20↑	Present/Absent/NE	Absent	irSD

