↓100 ↓≥30 ↓<30 to <20↑ NE	Present/Absent/NE	Present	irPD ^b
↓100 ↓≥30 ↓<30 to <20↑ NE	Unequivocal progression	Any	irPD ^b
↑≥20 from nadir	Any	Any	irPD ^b
NE	Present/Absent/NE	Absent	irNE ^b

irCR = immune-related complete response, irNE = immune-related not evaluable, irPD = immune-related progression disease, ir PR = immune-related partial response, irSD = immune-related stable disease, NE = Not evaluable, irRECIST = immune-related Response Evaluation Criteria in Solid Tumors SOD = sum of diameters

a: Decreases assessed relative to baseline, including measurable lesions only.

b: Assuming response (irCR) and progression (irPD) are confirmed by a second, consecutive assessment at least 4 weeks apart.

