5.4 Efficacy Analyses

Tumor response will be assessed by both immune-related RECIST (irRECIST) and modified version of RECIST 1.1 criteria (mRECIST 1.1) per investigator assessment, and by irRECIST, mRECIST 1.1 and RECIST 1.1 per independent imaging review. All efficacy analyses will be performed on the Full Analysis Set for the specific cohort analysis set for EC, RCC and other cohorts. Tabular summary of key features of the efficacy analyses is described in [Appendix 12.5](#) (Summary of Efficacy Analyses). Tumor assessments and overall response to the treatment according to irRECIST are presented in [Appendix 13.1](#).

The best overall response (BOR) is determined once all the data for the subject is known. For this study, a confirmation of complete responses or partial responses is required for both irRECIST and modified RECIST 1.1; and following irRECIST, a confirmation of progression due to a tumor burden is required unless it is per investigator's discretion if the subject was

clinically unstable. The confirmation assessments should be made ≥ 4 weeks later. The BOR is determined by sequentially checking two adjacent assessments with ≥ 4 weeks apart (and with a few special cases). As an example if a subject had a stable disease at the timepoint 1, a partial response at the timepoint 2, a complete response at the timepoint 3, and another complete response at the timepoint 4, then the BOR for this subject is complete response, which was confirmed at the timepoint 4.

To program the BOR per irRECIST: (1) the tumor response data collected via both irRECIST and mRECIST 1.1 CRFs will be used; (2) any further response assessments after the second PD (confirmed PD per irRECIST) identified under irRECIST should not be considered for the BOR determination, however they should be presented in the data listings; (3) all tumor assessments as long as the subjects did not start a new anti-cancer therapy should be considered; (4) if there are more than 1 consecutive missing tumor assessments, all assessments afterward should not be considered for the determination of BOR (also see [Section 5.4.3](#) for PFS). The BOR per irRECIST is defined as follows. [Table 4](#) lists general rules in the derivation of BOR with two consecutive tumor response results (with a few special cases, see Table 4).

- **CR**

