Nontarget Lesion Assessment	Nontarget lesions are evaluated qualitatively as present, absent, not evaluable (NE) or unequivocal progression. The response of nontarget lesions primarily contributes to the overall response assessments of CR. Nontarget lesions do not affect PR and SD assessments. Only a massive and unequivocal worsening of nontarget lesions alone, even in the presence of stable disease or a partial response in the target lesion is indicative of PD. CR is not possible unless all non-target lesions are absent.
Definition of New lesion	Any lesion which was not recorded at baseline. There is no minimum size criteria to identify a new lesion and clinical judgment must be used by the PI. 
 • May include a lesion in an anatomical location that was not scanned at baseline (i.e. brain) • Should be unequivocal and not due to differences in scanning technique • If equivocal, should be assessed at next timepoint; if present, PD is the date the lesion was first seen (not the date confirmed)
3. irRECIST Overall Tumor Assessment	
CR	
 • Complete disappearance of all measurable and nonmeasurable lesions (from baseline) and there are no unequivocal new lesions (unconfirmed CR). • Lymph nodes must decrease to < 10 mm in short axis. • Confirmation of response is required ≥ 4 weeks later, preferably at next time point, to be considered a confirmed CR.
PR	
 • If the SOD_{timepoint} of TLs decreases by $\geq 30\%$ compared to SOD_{baseline} and there are no unequivocal new lesions, and no progression of nontarget disease, it is an PR (unconfirmed). • Confirmation is required ≥ 4 weeks later, preferably at next time point, to be considered a confirmed PR.
SD	
Failure to meet criteria for CR or PR in the absence of PD.
 
 • If the sum of the TLs and the status of the nontarget lesions do not reach the criteria to meet PR or PD (increase $\geq 20\%$ and at least 5 mm absolute increase in SOD compared to nadir[†]) the response is SD. • SD = neither 30% decrease compared to SOD_{baseline} or 20% increase and at least 5 mm absolute change compared to nadir. • †SOD_{nadir}: Lowest measure SOD of TLs at any time point from baseline onward.
PD	Minimum 20% increase and a minimum 5 mm absolute increase in SOD compared to nadir, or PD for nontarget lesion(s) or unequivocal new lesion(s).

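### The irRECIST derivation table omits the 5 mm condition that the progression and stable-disease definitions in the same appendices require

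*Protocol*

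**What the plan says.** **Definitions.** Protocol Appendix 1 gives irPD as "Minimum 20% increase and a minimum 5 mm absolute increase in SOD compared to nadir, or irPD for nontarget lesion(s) or unequivocal new lesion(s"). The irSD entry just above it repeats both conditions: the percentage rise counts only together with the absolute one ("and at least 5 mm absolute increase in SOD compared to nadir"). SAP 13.1 carries the same definitions, labelled PD and SD.

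**Table.** The table of overall responses that closes each appendix has a target-lesion column expressed as percentage change in SOD. Its last target-lesion progression row reads, after an upward arrow, "≥20 from nadir", with any nontarget status and any new-lesion status. The irSD/SD row runs from a decrease under 30% to an increase under 20%. One footnote says that decreases are measured from baseline, and the other concerns confirmation. Neither mentions 5 mm.

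**Small lesions.** Both appendices cover small residual lesions: "If target lesion is too small to measure, a default value of 5mm should be entered on eCRF", and "If target lesion is 5-10mm, actual diameter should be entered in the eCRF".

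**Use.** Under Protocol 9.5.1.3, investigators base treatment decisions on irRECIST, and "If repeat imaging confirms irPD, subjects will be discontinued from study treatment". For programming best overall response (BOR), SAP 5.4 states that "the tumor response data collected via both irRECIST and mRECIST 1.1 CRFs will be used".

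**The concern.** One scan can get two answers from one appendix. Growth of at least 20% but under 5 mm is not target-lesion progression by the definition, yet it is by the table. The 5 mm floor keeps small measurement differences in small lesions from being called progression, and the table drops it for the subjects it protects: those with low-volume disease or deep shrinkage.

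Two things are mainly at stake. First, a subject could be taken off treatment for progression that the definition excludes. Second, the progression date used for PFS and DOR could be too early. SAP 5.4 dates PD at the first PD scan once the next scan confirms it, or if no repeat scan is done. Because the SAP builds BOR from responses on the CRFs and describes no recalculation from diameters, a response read off the wrong rule would pass through to the analysis.

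**Working it through.** The plan gives no figure to reproduce, so the check compares the two rules.

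**Inputs.** Progression definition and table row: Protocol Appendix 1 and SAP 13.1. Smallest eligible non-nodal lesion, 10 mm: Protocol 9.3.1, criterion 3. Default entry, 5 mm: Appendix 1. Scans at Weeks 6, 12, 18 and 24: Protocol 9.5.2.1, Table 9. BOR rules: SAP Table 4.

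**Formulas.** Let n be the nadir SOD and S the current SOD, in mm.
- Table: progression if S ≥ 1.2n.
- Definition: progression if S ≥ max(1.2n, n + 5).
- They disagree on 1.2n ≤ S < n + 5, which is non-empty only if 0.2n < 5, so n < 25 mm.

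| Nadir n | Table: progression from | Definition: progression from | Growth needed, table vs definition |
|---|---|---|---|
| 5 | 6 | 10 | 1 vs 5 mm |
| 10 | 12 | 15 | 2 vs 5 mm |
| 12 | 14.4 | 17 | 2.4 vs 5 mm |
| 15 | 18 | 20 | 3 vs 5 mm |
| 20 | 24 | 25 | 4 vs 5 mm |
| 25 | 30 | 30 | no difference |

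A nadir below 25 mm is reachable, since a single 10 mm lesion qualifies and a vanishing one is entered as 5 mm.

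**Treatment and PFS.** Baseline 25 mm; Weeks 6/12/18 give 20/24/24 mm.
- Week 6: 20/25 = 0.80, a 20% fall, irSD.
- Week 12: 24/20 = 1.20, a rise of 20% and 4 mm; 24/25 = 0.96, so 4% below baseline. irSD by the definition, irPD by the table.
- Week 18: the same values, so the table's irPD is confirmed. Confirmation is judged by the same threshold and does not filter out a persistent small rise.
- Result by the table: discontinuation at Week 18 and a PFS event dated Week 12. By the definition: neither. BOR is SD either way, so ORR does not change.

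**DOR.** The subject must first respond. At baseline 25 mm, a response needs S ≤ 0.70 × 25 = 17.5 mm. With 17.5 mm at Weeks 6 and 12, irPR is confirmed. The table then calls progression from 1.2 × 17.5 = 21 mm, the definition from 17.5 + 5 = 22.5 mm. If Weeks 18 and 24 are both 21 mm (21/25 = 0.84, no longer irPR), the definition gives irSD and the response continues; the table ends DOR at Week 18. BOR is PR either way.

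**BOR.** Baseline 30 mm; 12/15/15 mm.
- Week 6: 12/30 = 0.40, irPR.
- Week 12: 15/12 = 1.25 (25%, 3 mm) and 15/30 = 0.50. By the definitions this is irPR and not irPD, so BOR is PR.
- By the table, Week 12 fits two rows: a decrease of at least 30% (irPR) and a rise of at least 20% from nadir (irPD). If the irPR row is used, BOR is PR. If the irPD row is used, PR followed by PD gives SD under SAP Table 4.
- If the scans are 12/15/14/14 mm, then 14/12 = 1.167 is below the table's threshold, the last two scans are irPR under both rules, and BOR is PR either way.

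**The case against.** The best defence is that the table is shorthand. Its target column is in percentages, so it has no place for a millimetre condition, and it mainly shows how target, nontarget and new-lesion findings combine. It already needs the definitions elsewhere: irCR appears as a 100% decrease, although the irCR definition counts nodes under 10 mm as resolved. The full progression rule appears three times in the text before the table (twice under irSD, once under irPD), and the listed key changes for irRECIST include none to the progression threshold. Withdrawal is not automatic either: the investigator has discretion at first progression, and the sponsor can be asked about continuing after confirmed progression when benefit is exceptional.

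This lowers the practical weight, and many sites probably follow the definitions. It does not remove the conflict. Two adjoining categories omit the condition in two documents, so the table sets a complete percentage-only boundary, and nothing says that the text governs.

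A reader might go further and infer that the table biases the primary endpoint, ORR(Week 24), or that regrowth from nadir must outrank a partial response. The documents do not support either inference. Where the two table rows do not overlap, as in the first two examples, BOR is unchanged. BOR moves only where the SOD is still at least 30% below baseline, so that the irPR row fits too. The irPR definition excludes new lesions and nontarget progression; it is silent on target regrowth, and no sentence ranks the two. The case must also have a response not yet confirmed by two scans, regrowth inside the narrow gap, and no later pair of responding scans before progression is confirmed.

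**Conclusion.** The concern holds: the table is wrong as written, in both documents, and the priority is low. The conflict is confined to nadir SOD below 25 mm with growth of at least 20% but under 5 mm. Its main consequences are possible premature discontinuation and earlier progression dates for PFS and DOR. An effect on BOR or ORR(Week 24) is possible but conditional on an unstated ranking. One reclassified subject would be 1/20 = 5.0 points in a cohort of 20 and 1/120 = 0.83 points in one of 120, but that is the weight of any single subject, not an estimate of harm. Sample size, power and alpha are not affected.

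The conclusion assumes that some sites apply the table literally, and that the upper end of the stable-disease row is measured from nadir, as in the irSD definition and the progression row. How many subjects fall in the gap cannot be derived from the documents. SAP 13.5 adds an independent irRECIST reading of ORR(Week 24) for the endometrial and renal cohorts; the other four cohorts have only the investigator reading of that endpoint.

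**What to change.** In Protocol Appendix 1 and SAP 13.1:
- Change the progression row to *↑ ≥20% and ≥5 mm absolute increase from nadir*.
- Extend the stable-disease row to growth from nadir under 20% or under 5 mm, when partial response is not met.
- A footnote with the same content would serve equally well.

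Do not add a rule that progression outranks partial response as part of this correction. It would go beyond the irPR definition and would apply at any nadir, not only below 25 mm.

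Optionally, program a check on the recorded target-lesion diameters that flags responses inconsistent with the definition and sends a query to the site. It should not overwrite the investigator's response, because BOR is built from the CRF responses.

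The cost is two table rows or one footnote in each of two appendices, plus, if the check is adopted, one edit check and the queries it raises. The diameters are already entered on the eCRF, so no new data are needed and the check can be run on data already collected.

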Appendix 2 Eastern Cooperative Oncology Group Performance Status (ECOG-PS)

Scale	Performance Status
0	Fully active, able to carry on all pre-disease performance without restriction
1	Restricted in physically strenuous activity but ambulatory and able to carry out work of a light or sedentary nature (eg, light house work, office work)
2	Ambulatory and capable of all self-care, but unable to carry out any work activities. Up and about more than 50% of waking hours
3	Capable of only limited self-care, confined to bed or chair more than 50% of waking hours
4	Completely disabled. Cannot carry on any self-care. Totally confined to bed or chair.
5	Dead

Adapted from [Oken MM, et al. Am J Clin Oncol. 1982;5:649-55.](#)

